### 5.8.2 Adverse events

All Adverse events during the course of the study will be coded using the medical dictionary of regulatory activities (MedDRA) current at the start of the study and summarised by treatment group. AEs will be summarised by treatment, primary system organ class (SOC), preferred term (PT), relationship assessment and severity.

All solicited AEs identified via separate phone calls for the US will also be entered in the general AE section of the eCRF. Therefore, no separate analysis will be conducted.

The SOCs as well as the PTs within each summary table will be sorted by frequency in the total column in decreasing order.

AEs will be reported separately as pre-treatment or screening period AEs (any AE occurring prior to the first injection of study medication) and treatment emergent AEs (any AEs after first injection of study medication).

In general, all adverse events will be listed by treatment group, subject number, and period. For AE onset and end dates, the study day relative to the first injection will be listed.

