#### 5.8.2.1. Definitions related to adverse events

Pre-Treatment adverse event: Any AE with date and time of onset prior to the first injection of study medication. Pre-treatment AEs might also be termed Screening Period AEs.

Treatment emergent AE (TEAE): Any AE with date and time of onset after first injection of study medication. In case of (partially) missing date or time that could indicate a TEAE, it will be analysed as treatment emergent.

TEAEs during the treatment period: Any AE with date and time of onset after first injection of study medication and up to and including date of last injection of study medication + 28 days.

Adverse Drug Reactions (ADRs): Any AE that is possibly, probably or definitely related to study medication or the assessment of the relationship to study medication is missing as reported in the eCRF.

Adverse events related to study procedure: Any AE that was documented with causal relationship to a study procedure of “yes” in the eCRF.

Adverse events of special interest (AESI): Any AE that was documented as “AESI confirmed by Adjudication Committee” in the eCRF.

Local AE: Any AE that is documented with the category “Local (injection site) adverse event” in the eCRF.

Systemic AE: Any AE that is documented with the category “Systemic adverse event” in the eCRF.

Other AE: Any AE that is documented with the category “Other adverse event” in the eCRF, i.e. any adverse event that is neither local nor systemic.

AEs leading to premature discontinuation of treatment: Any AE for which action taken is documented as “Permanent discontinuation of the IMP” in the eCRF.

AEs leading to temporary discontinuation of treatment: Any AE for which action taken is documented as “Temporary discontinuation of the IMP” in the eCRF.

AEs leading to premature discontinuation of study: for which action taken is documented as “Withdrawal from the Study” in the eCRF.

Duration of adverse event (expressed in [days]) is calculated as follows:

- End date/time of AE – onset date/time of AE
- In case of missing onset time or missing end time: end date of AE – onset date of AE + 1
- In case of (partially) missing onset date or (partially) missing end date no calculation will be done
- In case of ongoing end date/time (outcome = recovering, not recovered or unknown), date of study termination will be used as documented at the end of the study page or the early termination page of the eCRF.

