#### **5.8.2.3. Overview summary tables for adverse events**

An overview summary of the following AE types will be provided, presenting number and percentage of subjects experiencing at least one AE of the respective AE type in each treatment group as well as the corresponding number of events.

- Any AE
- Any ADR
- Any severe AE
- Any severe ADR
- Any AE of special interest
- Any serious AE
- Any serious ADR
- Any non-serious AE
- Any AE leading to premature discontinuation from treatment
- Any AE leading to temporary discontinuation from treatment
- Any ADR leading to premature discontinuation from treatment
- Any ADR leading to temporary discontinuation from treatment
- Any AE leading to premature discontinuation of study
- Any ADR leading to premature discontinuation of study
- Any local TEAE
- Any systemic TEAE
- Any other TEAE, not classified as local or systemic AE

Furthermore, the number and percentage of subjects with AEs, ADRs and severe AEs after each injection will be summarized by treatment group, differentiating whether the AE occurred within 24 hours after injection, after 7 days of injection or thereafter, including only TEAEs within the treatment period.

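### The SAP's ADR definition and several AE table rows lack a treatment-emergent limit, so pre-injection events could be counted by arm, and as drug reactions when the relationship is blank

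*SAP*

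**What the plan says.** Section 5.8.2.1 of the SAP splits AEs by onset. A pre-treatment AE is "Any AE with date and time of onset prior to the first injection of study medication". A TEAE is "Any AE with date and time of onset after first injection of study medication. In case of (partially) missing date or time" that could point to a treatment-emergent event, in which case it is analysed as one. The ADR definition in the same list uses neither category: "Any AE that is possibly, probably or definitely related to study medication or the assessment of the relationship to study medication is missing".

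Section 5.8.2 gives the general rule: "AEs will be reported separately as pre-treatment or screening period AEs" on the one hand and treatment-emergent AEs on the other. The same section opens by saying that all AEs during the study are coded and summarised by treatment group.

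Section 5.8.2.3 specifies an overview table "presenting number and percentage of subjects experiencing at least one AE of the respective AE type in each treatment group". Most rows are labelled AE or ADR. Only the local, systemic and other rows carry the limit, for example "Any other TEAE, not classified as local or systemic AE". The table by injection at the end of that section is explicitly confined to TEAEs in the treatment period.

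Section 5.8.2.2 limits some SOC/PT rows to treatment-emergent events and leaves others as plain ADRs or plain local, systemic and other AEs.

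**The concern.** The protocol's schedule of activities records AEs from Visit 1. The skin prick test and a conjunctival provocation test are done at screening, before any injection. A further provocation test is scheduled at Visit 2, the visit of the first injection. Pre-injection AEs can therefore exist in subjects who go on to be treated.

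For such an event, relationship to study medication has no meaning, and the field might be left blank. Counting a blank as related is a reasonable conservative rule after dosing. Before dosing, it labels as a drug reaction something the drug could not have caused.

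The first safety endpoint in the protocol is the frequency, severity and relationship of AEs to treatment. Two things are at stake:

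- **Consistency.** ADRs may fail to be a subset of TEAEs. For a given preferred term, the ADR table could then show more subjects than the TEAE table, and the any-AE row would not reconcile with the TEAE tables.
- **Contrast.** Events unrelated to treatment, added to every arm, pull the active and placebo rates together.

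**Working it through.** **Step 1: count the rows.** The SAP states no figure that bears on this point, so the first check is a comparison of row labels with definitions.

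| Table | Rows | Limited to treatment-emergent | Not limited |
|---|---|---|---|
| Overview, 5.8.2.3 | 17 | 3 (local, systemic, other) | 8 AE + 6 ADR = 14 |
| SOC/PT, 5.8.2.2 | 14 | 6 | 5 ADR + 3 (local, systemic, other) = 8 |

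The local, systemic and other rows are limited in one section and not in the other. Serious AEs are treatment-emergent in the first list of 5.8.2.2, but the severity and relationship display in that section refers to all SAEs.

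**Step 2: find the rows that a pre-injection event can realistically reach.** Of the 14 unrestricted overview rows:

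- 4 concern permanent or temporary discontinuation of the IMP, which is hard to attach to an event before any IMP.
- 2 concern withdrawal from the study. A subject withdrawn before dosing is not in the Safety Set.

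That leaves 14 − 4 − 2 = 8 rows: any, severe, serious and non-serious AE; any, severe and serious ADR; and AESI, which also needs confirmation by the Adjudication Committee. In 5.8.2.2, the local row means injection-site events and so in effect needs an injection.

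**Step 3: illustrate the size for ADRs.** The documents give no ADR rates, no rate of screening AEs and no rate of blank relationships, so all inputs are assumptions. Let *p* be the true ADR rate in an arm (40% on PQ Grass, 15% on placebo). Let *s* be the proportion of treated subjects with a pre-injection AE whose relationship is blank, equal across arms and independent of later ADRs. Then:

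reported rate = 1 − (1 − *p*)(1 − *s*), and reported difference = (0.40 − 0.15)(1 − *s*).

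For *s* = 1%: 1 − 0.60 × 0.99 = 0.406 and 1 − 0.85 × 0.99 = 0.1585, so the risk ratio is 0.406/0.1585 = 2.56.

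| *s* | PQ Grass | Placebo | Risk ratio | Difference (points) |
|---|---|---|---|---|
| 0 | 40.0% | 15.0% | 2.67 | 25.0 |
| 1% | 40.6% | 15.9% | 2.56 | 24.75 |
| 2% | 41.2% | 16.7% | 2.47 | 24.5 |
| 5% | 43.0% | 19.3% | 2.23 | 23.75 |
| 10% | 46.0% | 23.5% | 1.96 | 22.5 |
| 20% | 52.0% | 32.0% | 1.63 | 20.0 |

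**Step 4: the any-AE row.** Here a blank relationship is not needed, so the relevant proportion is that of treated subjects with any pre-injection AE, which is at least *s*. With assumed TEAE rates of 60% and 40%, a proportion of 10% gives 1 − 0.40 × 0.90 = 64% and 1 − 0.60 × 0.90 = 46%. A proportion of 20% gives 68% and 52%.

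**The case against.** The best defence is that section 5.8.2 is the parent of 5.8.2.1 to 5.8.2.3. Its rule that pre-treatment and treatment-emergent events are reported separately can be read as governing every table below it. On that reading, a row label that says AE is only shorthand. This has force. A reader might infer from the tables that the plan definitely counts screening events by arm, and the documents do not support so flat a statement.

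The defence does not remove the problem, however. If the general rule already limited every row, the TEAE labels on three overview rows and the explicit limit on the by-injection table would be largely redundant. No table in 5.8.2.2 or 5.8.2.3 is assigned to pre-treatment AEs. The ADR definition itself has no onset condition under either reading.

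Other points on that side stand and narrow the concern:

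- Screen failures enter no AE summary (section 4.1), so only treated subjects matter.
- The by-injection table is already correct, ADRs included, and the TEAE tables by SOC and PT are available whichever way the overview is programmed.
- Section 4 requires the data to be checked and relevant queries answered before analysis, so few blanks may remain.
- Safety analysis is descriptive, with no test or decision rule on AEs, and pre-injection events are balanced across arms in expectation.

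A reader might also infer that skin prick or provocation reactions will routinely become ADRs. That would require the relationship field to be blank or marked as related. The documents do not say how often that happens, or whether the eCRF allows it.

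**Conclusion.** The concern holds as a defect in a stated rule and a conflict between sections. The ADR definition admits a pre-injection event with a blank relationship, and the tables in 5.8.2.2 and 5.8.2.3 do not consistently apply the separation announced in 5.8.2. Two programmers following this SAP could produce different overview tables.

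The consequence is dilution and failure to reconcile, with no bias towards a particular arm's event count. Its size is unknown. Under the assumed rates, the risk ratio stays close to its true value if such events are rare (2.56 to 2.47 at 1% to 2% of subjects) and falls to 1.63 only at 20%. Nothing in the documents supports the upper end of that range, so a large distortion should not be inferred. The inconsistency between ADR and TEAE counts needs only one such event.

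**What to change.** - **5.8.2.1:** define an ADR as any TEAE that is possibly, probably or definitely related to study medication, or whose relationship is missing. The missing-counts-as-related rule then applies only after the first injection.
- **5.8.2.2 and 5.8.2.3:** restrict every row to TEAEs and label it so, including the SAE entry in the severity and relationship display and the local, systemic and other rows.
- **Pre-treatment AEs:** report them in one separate table, as 5.8.2 intends.

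The cost is a change of SAP wording and one programming filter. No new data are needed.

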#### 5.8.2.2. Summary tables for analysis of adverse events

The number and percentage of subjects with

- TEAEs
- ADRs
- treatment emergent serious adverse events (SAEs)
- serious ADRs
- treatment emergent adverse events of special interest (AESIs)
- TEAEs leading to premature discontinuation of treatment
- ADRs leading to premature discontinuation of treatment
- TEAEs leading to temporary discontinuation of treatment
- ADRs leading to temporary discontinuation of treatment
- TEAEs leading to premature discontinuation of study
- ADRs leading to premature discontinuation of study
- local AEs
- systemic AEs

- other AEs, not classified as local or systemic AEs

will be summarised by treatment group, MedDRA SOC and PT.

For the analysis of the severity and the relationship of AEs, the worst severity and the strongest relationship per subject and type of AE will be used. The number and percentage of subjects with at least one AE by MedDRA SOC, PT and severity/relationship will be displayed only for

- all TEAEs
- all ADRs
- all serious adverse events (SAEs).

#### **5.8.2.3. Overview summary tables for adverse events**

An overview summary of the following AE types will be provided, presenting number and percentage of subjects experiencing at least one AE of the respective AE type in each treatment group as well as the corresponding number of events.

- Any AE
- Any ADR
- Any severe AE
- Any severe ADR
- Any AE of special interest
- Any serious AE
- Any serious ADR
- Any non-serious AE
- Any AE leading to premature discontinuation from treatment
- Any AE leading to temporary discontinuation from treatment
- Any ADR leading to premature discontinuation from treatment
- Any ADR leading to temporary discontinuation from treatment
- Any AE leading to premature discontinuation of study
- Any ADR leading to premature discontinuation of study
- Any local TEAE
- Any systemic TEAE
- Any other TEAE, not classified as local or systemic AE

Furthermore, the number and percentage of subjects with AEs, ADRs and severe AEs after each injection will be summarized by treatment group, differentiating whether the AE occurred within 24 hours after injection, after 7 days of injection or thereafter, including only TEAEs within the treatment period.

#### **5.8.3 Safety laboratory**

Blood samples for chemistry and haematology assessments will be collected at Visit 1 and Visit 15. Additionally, study sites will perform urine dipstick testing. In case of abnormal

findings, urine samples will be sent to the central laboratory for further analysis.

The laboratory tests that will be performed by the central laboratory are presented in Table 5. Laboratory test results and related normal ranges will be provided to investigators for review to assess subject eligibility and subject safety during the study.

**Table 5: Safety Laboratory Assessments**

Serum Chemistry	Glucose, Sodium, Uric acid, Urea, Potassium, Calcium, Creatinine, Chloride, Total protein, Phosphorus, Cholesterol, Albumin, Total Bilirubin, Alkaline phosphatase, LDH, AST, ALT, GGT, CRP
Haematology	Haemoglobin, haematocrit, total WBC and differentials, total RBC, RBC indices, and platelet count.
Urinalysis (using a urine dip-stick)	pH, Protein, Glucose, Ketones, Bilirubin, Blood, Nitrite, Urobilinogen, Leukocytes.

Abbreviations: ALT = alanine aminotransferase; AST = aspartate aminotransferase; CRP = C-reactive protein; GGT = gamma-glutamyl transferase; LDH = lactate dehydrogenase; RBC = red blood cells; WBC = white blood cells.

Summary tables will be created for serum chemistry and haematology.

For urinalysis, a frequency table will be created summarizing the overall sample.

#### 5.8.4 Vital signs

Vital signs (systolic and diastolic blood pressure, pulse rate, respiratory rate, and body temperature) will be measured after the subject has been in the supine position for at least 5 minutes at Visit 1 to Visit 15.

Summary statistics will be created per vital sign parameter and visit/timepoint (pre- and post-injection) for all scheduled treatment visits by treatment group including the absolute values per visit/timepoint and the absolute change from baseline.

#### 5.8.5 Physical examination

A complete physical examination include assessment of the following: general appearance, skin, head, neck, eyes, ears, nose, throat, lymph nodes, abdomen, musculoskeletal, cardiovascular, respiratory and neurological systems. Rectal, breast, pelvic, gynaecological, and/or urogenital examinations will not be performed. Complete physical examination will be performed at Visit 1 and Visit 15, or at the early termination visit if applicable.

#### 5.8.6 Other safety data

Pregnancy tests will only be performed on female subjects of childbearing potential on every visit (except 3 and 6 months safety follow-up calls). The corresponding results will only be listed by subject.

## **6 SOFTWARE AND STATISTICAL PROGRAMMING**

The statistical analysis will be performed using the SAS® statistical software package (Statistical Analysis System, Version 9.4 or higher) on a Windows Server 2016 System.

---

